## **9.7. Data Analysis**

### **9.7.1. Statistical Methods**

Detailed methodology for summary and statistical analyses of data collected in this study will be documented in a statistical analysis plan (SAP), which will be dated, filed and maintained by the sponsor. The SAP may modify the plans outlined in the protocol; any major modifications of primary endpoint definitions or their analyses would be reflected in a protocol amendment.

### **9.7.2. Data Summaries**

THAOS data will be available for analysis on 3 different levels: by patient, by individual survey site, and across survey sites.

The primary objective of the survey is to better understand the natural history of ATTR (hereditary and wild-type forms) and the progression of disease in this patient population. Analysis of clinical outcomes will be conducted on all enrolled patients with available data. Outcomes will be examined for the entire patient group, as well as through stratification of important variables that may affect outcomes (for example, but not limited to, TTR variant, age, race, gender, country of origin). Outcomes will include results of the key clinical, functional and QoL assessments used to define progression of disease.

Data will be summarized descriptively and modeled using appropriate statistical methodology.

THAOS physicians may use the THAOS electronic clinical database to obtain ongoing longitudinal data on their individual patients to assist them in following and caring for their patients. A physician can extract their individual survey site data for an individual or all patients enrolled at the survey site to identify trends in the data and/or assist in patient care and monitoring at their survey site.

THAOS physicians may request or share data across survey sites. A request may pertain to available information on patients with a newly identified TTR variant, or on a subset of patients to assist a THAOS physician with the clinical management of a patient (or patients), or to provide information pertinent to research interests across survey sites. Requests for data should be forwarded to the Sponsor for processing and will be promptly reviewed.

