### ATTR-PN

The hereditary forms of ATTR amyloidosis are autosomal dominantly inherited diseases with a variable penetrance that can affect multiple generations in a family and have a substantial impact on patients and their families. Val30Met (substitution of methionine for valine at position 30) is the most common mutation associated with ATTR-PN, with symptom onset usually in the third to fourth decade of life, depending on the mutation carried and the patient's ethnic background.

The main feature of ATTR-PN is progressive sensorimotor and autonomic neuropathy. Sensory neuropathy typically starts in the lower extremities followed by motor neuropathy within a few years. Autonomic neuropathy quite often accompanies the sensory and motor deficits. ATTR-PN is more frequently observed in certain areas of Portugal, Sweden, and Japan but has been identified throughout the world. Although penetrance varies greatly among geographic and ethnic foci, the outcome of the disease is invariably progressive and fatal. The lifespan for patients is severely shortened, with death occurring within a mean of 10-15 years from the first symptoms.

Disease-modifying therapies for ATTR-PN include TTR stabilizer tafamidis, orthotopic liver transplantation, RNA interference (RNAi)-based drugs, and transthyretin-directed antisense oligonucleotide drugs. Tafamidis meglumine was approved in the European Union (EU) on 16 November 2011 for the treatment of ATTR in adult patients with Stage 1 symptomatic polyneuropathy to delay peripheral neurologic impairment. Currently, it is approved for ATTR-PN in over 40 countries worldwide. Subsequently, Tegsedi (inotersen) and Onpattro (patisiran) for the treatment of hereditary ATTR amyloidosis in patients with polyneuropathy (ATTR-PN) have also been approved in the EU and US.

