### **5 ANALYSIS SETS/POPULATIONS**

Analysis of clinical outcomes will be conducted on all enrolled patients with available data. Outcomes will be examined for the entire enrolled patient group, as well as through subgroups based on important variables that may affect outcomes (for example, but not limited to, TTR data, phenotype, CCI [REDACTED]). Outcomes will include results of the key clinical, functional and Patient Reported Outcome assessments used to define progression of disease.

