#### **6.2.1 Survival**

Survival will be analysed as time from enrollment or first dose of tafamidis, for the untreated and tafamidis treated set respective until the time of death. Patients who are still alive at the end of the analysis period (start of tafamidis or end of follow-up in THAOS for the untreated set or last dose of tafamidis in the tafamidis treated set) will be censored.

CCI [Redacted]

[Redacted]

[Redacted]

[Redacted]

- [Redacted]
- [Redacted]
- [Redacted]

CCI [Redacted]

[Redacted]

[Redacted]

[Redacted]

PFIZER CONFIDENTIAL

[Redacted]

CCI

[Redacted]

[Redacted]

[Redacted]

CCI

[Redacted]

[Redacted]

[Redacted]

[Redacted]

[Redacted]

CCI

[Redacted]

[Redacted]

PFIZER CONFIDENTIAL

[Redacted]

CCI [Redacted]

CCI [Redacted]

[Redacted]

[Redacted]

[Redacted]

[Redacted]

[Redacted]

[Redacted]

- [Redacted]
- [Redacted]
- [Redacted]
- [Redacted]

PFIZER CONFIDENTIAL

[Redacted]

CCI [Redacted]

[Redacted]

[Redacted]

[Redacted]

- [Redacted]
- [Redacted]
- [Redacted]
- [Redacted]
- [Redacted]
- [Redacted]

[Redacted]

- [Redacted]
- [Redacted]

[Redacted]

[Redacted]

CCI [Redacted]

[Redacted]

[Redacted]

[Redacted]

CCI [REDACTED]

CCI [REDACTED]

CCI [REDACTED]

[REDACTED]

[REDACTED]

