## **8 STATISTICAL METHODOLOGY AND STATISTICAL ANALYSES**

### **8.1 STATISTICAL METHODS**

The key objectives of the survey are to better understand the natural history of ATTR (hereditary and wild-type forms) and the progression of disease in this patient population. Analysis of clinical outcomes will be conducted on all enrolled patients with available data. Outcomes will be examined separately for the untreated and tafamidis treated sets, as well as for appropriate subgroups within these set. Outcomes will include results of the key clinical, functional and QoL assessments used to define progression of disease.

Data will be summarized descriptively.

Continuous variables will be summarized using descriptive statistics ie, number of non-missing values and number of missing values [ie, n (missing)], mean, median, standard deviation (SD), minimum, maximum and 10th and 90th percentile.

Qualitative variables will be summarized by frequency counts and percentages. Unless otherwise specified, the calculation of proportions will be based on non-missing values.

In case the analysis refers only to certain visits, percentages will be based on the number of patients still present in the study at that visit, unless otherwise specified. Sample size in a subgroup needs to be at least 10 in order to have sufficient data to provide descriptive statistics, listings will be provided for smaller subgroups.

Kaplan-Meier estimates (product-limit estimates) will be presented including the median time with two-sided 95% confidence intervals (CIs), if the number of events are at least 5.

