### 8.2.6 Safety Analyses

#### Survival Analyses

Mortality will be analysed using the Kaplan Meier method with median survival times (if estimable) and 95% CIs if the number of events are at least 5.

Mortality will be summarized and presented by plots for the following sets: tafamidis treated set by phenotype at enrollment and overall, tafamidis untreated set by phenotype at enrollment and overall, CCI and either predominantly cardiac or mixed phenotype at enrollment, tafamidis treated set for patients who had severe hepatic impairment at baseline, tafamidis

untreated set by their liver transplantation status (liver transplant prior to enrollment/liver transplant after enrollment/no liver transplant), tafamidis treated set by liver transplantation status (liver transplant prior to first dose of tafamidis/liver transplant after the first dose of tafamidis/no liver transplant).

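### Time-to-death is planned only in two sets cut at tafamidis decisions, with no all-enrolled curve; the untreated curve is likely too high for patients asymptomatic at enrollment and of uncertain direction in symptomatic phenotypes

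*Protocol*

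**What the plan says.** **Population for outcomes.** Protocol 9.7.2 states "Outcomes will be examined for the entire patient group, as well as through stratification of important variables that may affect outcomes". SAP 5 says the same of the enrolled group: "Outcomes will be examined for the entire enrolled patient group, as well as through subgroups based on important variables that may affect outcomes". SAP 8.1 differs: "Outcomes will be examined separately for the untreated and tafamidis treated sets".

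**Which outcomes.** In Protocol 9.7.2 the general statement is followed by "Outcomes will include results of the key clinical, functional and QoL assessments used to define progression of disease". Survival is not named there. The SAP places it under safety endpoints (6.2.1).

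**Survival sets.** SAP 8.2.6 begins its list with "Mortality will be summarized and presented by plots for the following sets: tafamidis treated set by phenotype at enrollment and overall" and continues with the untreated set and subgroups of both sets. The Survival row of the SAP 8.2.8 grid has no mark under All enrolled. The Death row does, and the Deaths paragraph of 8.2.6 gives number, percentage, primary cause and ATTR-relatedness for all enrolled patients, with no time axis.

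**Censoring.** SAP 6.2.1 counts time from enrollment (untreated set) or first dose (treated set). Patients still alive are censored at the end of the analysis period, given as "start of tafamidis or end of follow-up in THAOS for the untreated set or last dose of tafamidis in the tafamidis treated set". SAP 5.2 excludes data after tafamidis is stopped from the untreated set.

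**Who starts tafamidis.** Protocol 9.1 says commercial treatment follows the product label. Protocol 7.1 describes tafamidis as "approved in the European Union (EU) on 16 November 2011 for the treatment of ATTR in adult patients with Stage 1 symptomatic polyneuropathy", and reports later approvals for cardiomyopathy in 2019-2020. SAP 5.4 has a separate phenotype group for asymptomatic variant carriers.

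**The concern.** Kaplan-Meier estimation assumes that patients censored at a given time have the same future risk as those who stay. Here a patient leaves the untreated set on starting a drug whose label is tied to symptomatic disease. A carrier who is well at enrollment contributes time while well and tends to leave soon after becoming ill. Splitting by phenotype at enrollment does not repair this, because onset comes later.

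A patient who starts tafamidis after enrollment is divided between the two sets, so no curve in this SAP follows that patient from enrollment to death.

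The stake is interpretation. Protocol 9.7.2 makes natural history and progression the primary objective. Protocol 8 and SAP 2.2 include overall survival with and without liver transplant among the objectives. Protocol 7.2 and SAP 2 expect the data to inform the effect of tafamidis on survival and possibly treatment guidelines. Readers will take the untreated curves as natural-history survival, and nothing in the visible text tells them which way those curves may be off.

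**Working it through.** The plan states no survival estimate, event count or sample size, so there is no figure to reproduce. The check compares true survival without the drug with the large-sample Kaplan-Meier value when patients are censored at tafamidis start.

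**1. Patients asymptomatic at enrollment**

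Inputs, per year:
- Death after onset, μ = 1/15 to 1/10. Protocol 7.1 (ATTR-PN) gives a mean of 10-15 years from first symptoms to death; an exponential distribution is assumed.
- Symptom onset, λ = 0.05 to 0.10 (assumed).
- Death before onset, b = 0.005 (assumed).
- Tafamidis start, τ = 0.2 to 1.0 after onset and zero before (assumed).

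Formulas:
- True survival: S(T) = e^(−(λ+b)T) + [λ/(λ+b−μ)]·[e^(−μT) − e^(−(λ+b)T)].
- Ratio of symptomatic to asymptomatic patients still untreated and at risk: r(t) = [λ/(μ+τ−λ−b)]·[1 − e^(−(μ+τ−λ−b)t)].
- Kaplan-Meier limit: exp(−∫₀ᵀ (b + μr)/(1 + r) dt).

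Example with λ = 0.10, μ = 0.10, τ = 0.5, T = 10:
- S = e^(−1.05) + 20·(e^(−1) − e^(−1.05)) = 0.350 + 20 × 0.01794 = 0.709.
- r(10) = (0.10/0.495)·(1 − e^(−4.95)) = 0.201. The death rate among those left at year 10 is (0.005 + 0.10 × 0.201)/1.201 = 0.021. With no removal at tafamidis start, r(10) = 1.025 and the rate is (0.005 + 0.1025)/2.025 = 0.053.
- The integral is 0.1805, so the curve reads e^(−0.1805) = 0.835, which is 12.6 points too high.

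10-year results over the range:

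| μ | λ | True | Censored KM, τ = 0.2 / 0.5 / 1.0 | Difference (points) |
|---|---|---|---|---|
| 1/15 | 0.05 | 84.9% | 88.4 / 91.0 / 92.7% | +3.5 / +6.0 / +7.7 |
| 1/15 | 0.10 | 77.6% | 82.6 / 87.1 / 90.3% | +5.0 / +9.4 / +12.6 |
| 1/10 | 0.05 | 80.9% | 85.6 / 89.1 / 91.5% | +4.6 / +8.1 / +10.5 |
| 1/10 | 0.10 | 70.9% | 77.5 / 83.5 / 87.9% | +6.6 / +12.6 / +17.1 |

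Every scenario is upward. With τ = 0 the difference is zero.

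**2. Symptomatic patients, early and advanced disease** (all rates assumed)

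Suppose tafamidis starts only in early disease and advanced patients stay untreated. Take early death 0.04, advanced death 0.20, progression 0.10, 70% early at entry and start at 0.5 per year. True 10-year survival is 34.3% and the censored curve reads 19.4%, a difference of −14.9 points. Censoring removes the lower-risk patients: at year 5 early disease makes up 57% of survivors without censoring and 15% of those still at risk with it.

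The range is −3.5 to −16.6 points over progression 0.10-0.20, death rates of 0.04 and 0.20 or 0.05 and 0.15 (early and advanced), 70-100% early at entry, and start 0.2-0.5.

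**3. Mixed cohorts** (onset 0.07, progression 0.15, death 0.005 / 0.04 / 0.20, start 0.5 in early disease only; all assumed)

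| Asymptomatic / early / advanced at entry | Difference at 10 years (points) |
|---|---|
| 50 / 35 / 15% | +7.4 |
| 30 / 40 / 30% | +1.8 |
| 0 / 70 / 30% | −11.0 |

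If starting is unrelated to risk (one homogeneous group, death 0.10, start 0.5), both values are 36.8% and there is no bias.

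**The case against.** **A reader might infer that natural-history survival is overstated throughout the untreated set.** The documents do not support that. The EU polyneuropathy approval cited in Protocol 7.1 is for Stage 1 disease. If early patients are treated and advanced ones are not, the untreated curve is too low. The documents give neither the case mix nor the pattern of starting, so the direction is not fixed outside the asymptomatic stratum.

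**A reader might infer a broken commitment.** That is also too strong. The general statements go on to name progression assessments, not survival, and Protocol 9.7.1 lets the SAP modify the plan. What stands is that SAP 5 and 8.1 disagree, which needs reconciling.

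**All-enrolled mortality is not wholly absent.** The crude death summary exists. It does not show survival over follow-up that began in 2007. SAP 2 also says separate plans cover publications and other uses, so the absence of a curve is established for this SAP only.

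**Rapid starting over ten years may be unrealistic.** Data collection began in December 2007, the EU approval came in November 2011, and the cardiomyopathy approvals cited came in 2019-2020. Much untreated time may predate them. This argues for the lower part of the range, which is why starts of 0.2 per year are included. It does not remove the bias.

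**The study is descriptive, the censoring rule is stated openly and curves are split by phenotype at enrollment.** All true. A Kaplan-Meier curve with a 95% confidence interval is still an estimate resting on non-informative censoring. Protocol 9.9 foresees confounding control and sensitivity analysis for loss to follow-up; the visible SAP text has nothing for censoring at tafamidis start.

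**Conclusion.** The point holds in limited form. SAP 5 and 8.1 conflict, and this SAP plans time-to-death only in sets cut at tafamidis start or last dose. Censoring of the untreated set is likely informative.

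For patients asymptomatic at enrollment the bias is upward, about 3.5 to 17 points at 10 years. Only the post-onset mortality comes from the documents, and it applies to polyneuropathy; onset, background mortality and start rates are assumptions. For symptomatic phenotypes the direction cannot be settled from the documents, and understatement is possible. A single statement that untreated survival is too high, or too low, would not be justified.

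The change should be made, because errors of opposite sign could sit side by side in the by-phenotype plots with nothing to tell the reader which applies.

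**What to change.** 1. Reconcile SAP 5 and 8.1 on the population in which outcomes are examined.
2. Add All enrolled to the Survival row of SAP 8.2.8 and to the Survival Analyses text of 8.2.6: time from enrollment to death or last known alive, by phenotype at enrollment, with no censoring at tafamidis start or stop. Label it *survival under actual care*. It includes treated time and does not recover untreated survival.
3. Label the untreated curves *censored at tafamidis start* and do not present them as unbiased natural-history survival.
4. Where data allow, add a sensitivity analysis for the untreated set using inverse-probability-of-censoring weights with age, genotype and time-updated disease status. Of these steps, only this one addresses the bias in untreated survival.

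**Cost.** One extra set of curves that mixes treated and untreated time, and a weighted analysis that may be imprecise. The variables are on the existing forms, but assessments are optional and visits roughly annual, so onset and tafamidis start may first appear at the same visit. Phenotype does not capture stage within symptomatic disease, so the weights may correct the symptomatic strata only in part; the report should say so. Study conduct does not change.

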### **9.7.3. Scientific Board**

The Scientific Board is comprised of a group of scientific and clinical experts in the field of amyloid disease who will provide scientific oversight and interpretation of the data originating from THAOS and its sub-studies. The role of the Board is to develop treatment recommendations and practice guidelines for patients with transthyretin amyloidosis based on findings from either the survey or external data. The roles and responsibilities of the Board are detailed in the THAOS Scientific Board Charter.

#### **9.7.4. Interim Analyses**

There is no formal interim analysis planned.

Safety data required as part of the European Medicines Agency RMP for tafamidis will be analyzed and submitted annually.

One or more data extracts will be performed annually in order to support ad hoc analyses for publications and for pricing and reimbursement.

### **9.8. Quality Control**

#### **9.8.1. Data Editing**

Data entered into the THAOS electronic clinical database will be automatically checked according to the database specifications, focusing on data critical for analysis, using limits set within the programming. Error messages will appear notifying the sites of discrepancies as they are identified or at the point of data signature. Data clarification requests may be generated and sent electronically to the THAOS sites. Completed requests will be returned to the electronic clinical database. All changes to the THAOS electronic clinical database will be tracked via an audit trail.

#### **9.8.2. Audits**

Local or international regulatory authorities, the IRB/EC, the Sponsor, or its designee, may request access to all patient consent forms, source documents, THAOS electronic data records, and other survey documentation for on-site audit or inspection. Direct access to these documents must be guaranteed by the investigator, who must provide support at all times for these activities.

#### **9.8.3. THAOS Electronic Clinical Database**

The investigator has ultimate responsibility for the collection and reporting of all clinical, safety, and laboratory data entered in the THAOS electronic clinical database from source documents (eg, hospital or physician patient charts), physical examinations, and patient reports. The investigator must ensure that the information is accurate, authentic/original, attributable, complete, consistent, timely (contemporaneous), enduring, and available when required.

### **9.9. Limitations of the Research Methods**

The observational nature of this study has the potential to introduce selection or ascertainment bias. The study population could be more heterogeneous. Confounding leads to biased estimates of associations of risk factors or treatment with outcome and thus impacts the validity of the conclusions from the study. Analytical methods (like matching, multivariate regression) would be used to control for confounding.

Other potential limitations to the validity of the study include missing data and loss to follow-up or censoring. Appropriate statistical methods would be employed to account for missing data and described in the SAP. Sensitivity analysis to assess the impact of loss to follow-up will also be explored.

## **9.10. Other Aspects**

Not Applicable.

## **10. PROTECTION OF HUMAN SUBJECTS**

### **10.1. Patient Information**

All parties will comply with all applicable laws, including laws regarding the implementation of organizational and technical measures to ensure protection of patient personal data. Such measures will include omitting patient names or other directly identifiable data in any reports, publications, or other disclosures, except where required by applicable laws.

Upon entry into THAOS, a patient will be assigned a unique patient number. This number is a combination of the site country identifier, the assigned site number, and the number given to a patient in order of enrollment at the site (eg, SE 01 005 is the fifth patient enrolled at the first participating site in Sweden). Each patient will be identified by this unique number. In order to maintain patient privacy, all databases, survey reports, and communications will identify the patient only by the unique patient number.

The personal data will be stored at the study site in encrypted electronic and/or paper form and will be password protected or secured in a locked room to ensure that only authorized study staff have access. The study site will implement appropriate technical and organizational measures to ensure that the personal data can be recovered in the event of disaster. In the event of a potential personal data breach, the study site shall be responsible for determining whether a personal data breach has in fact occurred and, if so, providing breach notifications as required by law.

To protect the rights and freedoms of natural persons with regard to the processing of personal data, when study data are compiled for transfer to Pfizer and other authorized parties, patient names will be removed and will be replaced by a single, specific, numerical code, based on a numbering system defined by Pfizer. All other identifiable data transferred to Pfizer or other authorized parties will be identified by this single, patient-specific code. The investigator site will maintain a confidential list of patients who participated in the study, linking each patient's numerical code to his or her actual identity. In case of data transfer, Pfizer will maintain high standards of confidentiality and protection of patients' personal data consistent with the clinical study agreement and applicable privacy laws.

